1.3.3 Phase I Dose-Finding and Pharmacokinetics

A total of 55 patients were enrolled in the dose escalation phase of study PLX06-02, including patients with metastatic melanoma (n=50), thyroid cancer (n=3), rectal carcinoma (n=1) and ovarian cancer (n=1). Several different capsule strengths and formulations were evaluated in this part of the study. Twenty-six patients received doses of vemurafenib ranging from 160 mg to 1120 mg b.i.d using the optimized drug formulation (referred to as micro-precipitated bulk powder [MBP] formulation) with greater bioavailability. With this optimized formulation, minimum efficacious exposures above the exposure identified in the preclinical models ($\geq 400\mu\text{M}\cdot\text{h}$) were achieved at 240 mg b.i.d. Vemurafenib MBP formulation has shown dose proportional increases in exposure across all cohorts, particularly from 240 to 960 mg b.i.d. Mean steady state exposure levels of vemurafenib (area under the plasma concentration-time curve, AUC_{0-24h}) in these dose cohorts ranged from 467.1 $\mu\text{M}\cdot\text{h}$ to 1324.6 $\mu\text{M}\cdot\text{h}$. The 960 mg b.i.d dose of vemurafenib achieved mean steady state exposure levels of 69.6 μM and 1324.6 $\mu\text{M}\cdot\text{h}$, for maximum plasma concentration (C_{max}) and AUC_{0-24h}, respectively.

An apparent mean half-life of ~90 hours (range, 30 to 145 hours) following multiple doses in patients receiving 960 mg bid in the melanoma extension cohort was determined based on the mean accumulation ratio of vemurafenib exposure between Day 1 and Day 15. With the twice-daily dosing regimen, all patients were exposed to relatively constant daily levels of the drug at steady state.

Dose-limiting toxic effects were not observed until a dose of 720 mg b.i.d. At the next highest dose given to one group of patients, 1120 mg b.i.d, four of six patients developed non-life threatening dose-limiting toxicity (DLT): three patients with Grade 3 rash (two of whom also had Grade 3 fatigue) and one patient with Grade 3 arthralgia. All events resolved with temporary drug interruption. In all cases, patients resumed treatment at lower doses of 720 mg b.i.d. One DLT, Grade 4 pancytopenia, was observed at 720 mg b.i.d. Upon resolution of the pancytopenia after 9 days of study drug interruption, the patient was rechallenged with vemurafenib at a lower dose of 360 mg b.i.d without recurrence of the pancytopenia. No new

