16. Fertile men and women must use an effective method of contraception during treatment and for at least 6 months after completion of treatment as directed by their physician. Effective methods of contraception are defined as those which result in a low failure rate (i.e., less than 1% per year) when used consistently and correctly (for example implants, injectables, combined oral contraception or intra-uterine devices). At the discretion of the Investigator, acceptable methods of contraception may include total abstinence in cases where the lifestyle of the patient ensures compliance. (Periodic abstinence [e.g., calendar, ovulation, symptothermal, postovulation methods] and withdrawal are not acceptable methods of contraception).
17. Absence of any psychological, familial, sociological, or geographical conditions potentially hampering compliance with the study protocol and follow-up schedule; those conditions should be discussed with the patient before trial entry

*For prostate cancer, ECD and/or LCH specific eligibility criteria as part of Cohort 7, see [Appendix 9](#) and [Appendix 10](#), respectively.

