4.4.1 Excluded Therapy and Potential Interactions with Concomitant Drugs

4.4.1.1 Excluded therapy

The following medications and treatments are not allowed while the patient is on the study:

- other anti-cancer therapies (except cetuximab for patients in Cohort 3b)
- concomitant alternative therapies and herbal preparations
- radiotherapy for the treatment of disease during the study; the exception will be limited field radiotherapy for palliative bone pain due to pre-existing bone metastasis if not considered a target lesion for RECIST assessments

However, medications primarily metabolized by CYP450 1A2, 3A4 and 2C9 enzymes, as well as those that strongly inhibit or induce the CYP 3A4 enzyme, should be used with caution when co-administered with vemurafenib.

[Appendix 2](#) includes a non-exhaustive list of typical examples of CYP1A2 and CYP3A4 substrates and CYP3A4 inducers and inhibitors.

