4.4.1.2.1 CYP3A4 substrates

In the CYP450 probe study NP22676, vemurafenib induced CYP3A4 activity in melanoma patients by approximately 2-fold, as evidenced by a parent-to-metabolite AUC ratio of 2.2 for midazolam in the presence vs. the absence of vemurafenib. This interaction was statistically significantly outside the customary no-effect boundary (0.8–1.25). Thus, medications predominantly metabolized via CYP3A4 may have decreased exposure when administered concomitantly with vemurafenib.

The clinical significance of this observation depends on the therapeutic index of the specific CYP3A4 substrate administered concomitantly with vemurafenib. If CYP3A4 substrates must be co-administered with vemurafenib, the Investigator should monitor the signs of reduced benefit of CYP3A4 drugs due to potential decrease in their plasma concentration. Doses of the concomitant CYP3A4 drug, but not the dose of vemurafenib, may be adjusted as necessary to alleviate the impact of drug interaction.

[Appendix 2](#) includes a non-exhaustive list of CYP3A4 substrates.

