4.4.1.2.2 CYP1A2 substrates

In the CYP450 probe study NP22676, vemurafenib inhibited CYP1A2 in metastatic melanoma patients by approximately 3-fold, as evidenced by a parent-to-metabolite AUC ratio of 0.32 for xanthine in the presence vs. the absence of vemurafenib. This interaction was statistically significantly outside the customary no-effect boundary (0.8–1.25). Similarly, other PK assessments have demonstrated drug-drug interactions between vemurafenib and caffeine that are consistent with CYP1A2 inhibition. **Thus, medications predominantly metabolized via CYP1A2 may have increased exposure when administered concomitantly with vemurafenib.**

The clinical significance of these observations depends on the therapeutic index of the specific CYP1A2 substrate administered with vemurafenib. The Investigator should assess the safety risk associated with a potential increase in plasma concentrations of any concomitantly administered, CYP1A2 metabolized drug. If there is a concern, doses of the concomitant CYP1A2 drug, but not the dose of vemurafenib, may be adjusted as necessary to alleviate the impact of drug interaction.

[Appendix 2](#) includes a non-exhaustive list of CYP1A2 substrates.

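### Criterion 16 offers hormonal methods to female patients as below-1%-failure contraception with no interaction caveat, although the protocol's own CYP3A4 text puts their reliability in doubt

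*Protocol*

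**What the plan says.** Criterion 16, worded the same in Section 4.2 and the synopsis, reads: "Fertile men and women must use an effective method of contraception during treatment and for at least 6 months after completion of treatment". The treating doctor gives direction on this. Effective methods are those with a failure rate below 1% per year under consistent and correct use, and the illustration is "for example implants, injectables, combined oral contraception or intra-uterine devices". The criterion mentions no drug interaction and does not refer to the interaction sections.

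Section 4.4.1.2.1 reports about 2-fold CYP3A4 induction in melanoma patients and concludes: "Thus, medications predominantly metabolized via CYP3A4 may have decreased exposure when administered concomitantly with vemurafenib". Its handling advice is that "the Investigator should monitor the signs of reduced benefit of CYP3A4 drugs due to potential decrease in their plasma concentration", and "Doses of the concomitant CYP3A4 drug, but not the dose of vemurafenib, may be adjusted as necessary". Section 4.4.1.1 says more generally that medications handled mainly by CYP1A2, CYP3A4 and CYP2C9 "should be used with caution when co-administered with vemurafenib".

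Appendix 2 places progesterone and estradiol in its CYP3A4 column, where the footnote says exposure may decrease. Estradiol also stands in the CYP1A2 column, where the footnote says exposure may increase. This matches Section 4.4.1.2.2, which states that "vemurafenib inhibited CYP1A2 in metastatic melanoma patients by approximately 3-fold".

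Section 5.4.1 and the schedules of assessments place the serum pregnancy test at screening only.

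**The concern.** The eligibility criterion endorses a class of methods that another part of the same protocol gives reason to question. A site that follows the examples as written can enrol a woman whose only contraception is an implant, an injectable or a combined pill and regard the below-1% requirement as met. Nothing in the criterion prompts the site to ask whether that figure still applies while she takes an inducer of CYP3A4.

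What is at stake is participant safety: an unintended pregnancy exposed to the study drug. Section 7.3.4.2.3 treats this as a real hazard, since it requires the drug to be stopped and the possible effects on the foetus to be discussed. Women from age 16 are eligible, and treatment is continuous until progression, so exposure can be long. The point concerns eligibility and safety wording and has no bearing on the statistical design.

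**Working it through.** No planned figure has to be reproduced. The check sets the relevant texts side by side.

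**1. The methods named.** Criterion 16 gives four examples. Reading implants, injectables and combined pills as hormonal makes three of four. Intra-uterine devices are left out because their type is not stated. This is a count of labels and does not measure lost reliability.

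**2. The interaction.** Section 4.4.1.2.1 concludes that CYP3A4 is induced about 2-fold and that substrate exposure may fall. It supports this with an AUC ratio of 2.2 described as parent to metabolite, which read literally points the other way; the CYP1A2 ratio of 0.32 in Section 4.4.1.2.2 has the same inversion. The point here uses only the protocol's explicit conclusion.

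**3. The link to sex steroids.**

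| Steroid in Appendix 2 | CYP3A4 column (exposure may fall) | CYP1A2 column (exposure may rise) | Direction |
|---|---|---|---|
| Progesterone | yes | no | down |
| Estradiol | yes | yes | unsettled |

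Progesterone is the clean case. The protocol does not name the hormones in any contraceptive product, so the step from progesterone to implants, injectables and pills is an inference. Section 4.4.1.2.1 calls the substrate list non-exhaustive, so a product's absence from it is no reassurance.

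**4. The safeguards, one by one.**
- Caution with substrates (Section 4.4.1.1): general, not linked to contraception, and not referred to in criterion 16.
- Watching for reduced benefit and adjusting the other drug's dose (Section 4.4.1.2.1): poorly suited to a contraceptive, where lost benefit would ordinarily show only as a pregnancy. That is reasoning, not something the protocol states.
- Awareness of drug interactions (Section 7.1): preventive, addressed to investigators and patients, and it points to Section 4.4 and Appendix 2; again not tied to contraception.
- Physician direction (criterion 16): helpful, but the physician is reading a list that presents these methods as adequate.
- Exclusion 18 (Section 4.3): covers unwillingness to use birth control, not an unreliable method.
- Pregnancy section (7.3.4.2.3): acts only after conception.
- Pregnancy testing: scheduled at screening only, so no scheduled on-treatment test would detect a failure.

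**5. How long a caveat should run.** Section 1.3.3 gives "An apparent mean half-life of ~90 hours (range, 30 to 145 hours) following multiple doses". Taking five half-lives as the time to elimination (an assumption; 0.5^5 = 3.1% remains):
- mean: 5 × 90 h = 450 h = 18.8 days
- shortest: 5 × 30 h = 150 h = 6.3 days
- longest: 5 × 145 h = 725 h = 30.2 days

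The existing period of at least 6 months (about 182 days) exceeds all three. The duration in criterion 16 is therefore not a defect, and a caveat can use it unchanged.

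**The case against.** The strongest reply is that this is a missing cross-reference and no contradiction. The binding requirement is a failure rate below 1% per year, the methods are only examples, and a physician who has read Sections 4.4 and 7.1 and Appendix 2 may reject a method he or she doubts. Section 7.1 matters here because it acts in advance and reaches patients too. In addition, no contraceptive is named as a substrate. Section 4.4.1.2.1 speaks only of drugs predominantly metabolised by CYP3A4, says exposure may fall, and makes the clinical importance depend on the therapeutic index of the particular drug. Section 7.4 defers to the Investigator's Brochure, and the consent pages are not available here, so patients may be advised elsewhere.

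Much of this stands as a limit on strength. A reader might infer that hormonal contraception has been shown to fail with vemurafenib, or that three of the four examples miss the 1% standard. The documents support neither, since they give no failure rate under induction and do not distinguish products, doses or routes. The reply does not remove the gap, however. Criterion 16 names the methods affirmatively, and none of the cautions mentions contraception. Advice elsewhere would not correct the criterion's wording. The protocol also gives drug-specific warnings on weaker evidence: Section 4.4.1.2.3 singles out warfarin after a rise of about 20% that lay within the no-effect boundary, whereas the CYP3A4 effect lay outside it.

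**Conclusion.** The point holds as an internal safety inconsistency worth correcting. On the protocol's own text, the reliability of hormonal contraception in female patients taking vemurafenib is in doubt, and criterion 16 does not say so.

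The conclusion rests on the stated induction, on progesterone's listing under CYP3A4 only, and on the inference that hormonal products share its fate. The size of any loss cannot be derived: the documents give neither a failure rate under induction nor the number of women using these methods.

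Two wider readings should be set aside. The post-treatment contraception period is not too short. Nor does the point reach female partners of male patients, who do not take vemurafenib. The trial's validity is not in question.

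**What to change.** Add to criterion 16, in Section 4.2 and in the synopsis, directly after the examples:

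> For female patients taking vemurafenib, hormonal contraceptives may be less effective because of possible CYP3A4 induction (see Section 4.4.1.2.1 and Appendix 2) and should not be relied on as the sole method; use a non-hormonal method with a failure rate below 1% per year (for example a non-hormonal intra-uterine device), or an additional non-hormonal method alongside the hormonal one as directed by the physician, during treatment and the existing post-treatment contraception period. This does not apply to female partners of male patients.

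The combined option is left to the physician because the documents give no failure rate for an added method. If the sponsor holds data showing no relevant interaction, citing them at criterion 16 would resolve the point equally well.

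The cost is two sentences in two places. Some women must change or add a method, and for longer than the roughly 6 to 30 days of drug elimination estimated above; the full period is used because the documents do not say when induction ends. Sample size, endpoints and analysis are unaffected.

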4.3 EXCLUSION CRITERIA

Exclusion Criteria:

1. Melanoma, papillary thyroid cancer or haematological malignancies (with the exception of multiple myeloma).
2. Uncontrolled concurrent malignancy (early stage or chronic disease is allowed if not requiring active therapy or intervention and is under control)
3. For MM, solitary bone or solitary extramedullary plasmacytoma as the only evidence of plasma cell dyscrasia
4. Active or untreated CNS metastases.
 - Patients with brain metastasis are eligible if asymptomatic, off corticosteroid therapy, and without evidence of disease progression in brain for \geq 2 months.
 - Patients with incidentally found brain metastases that are asymptomatic and for which no treatment is planned are also eligible.
5. History of or known carcinomatous meningitis

6. Concurrent administration of any anti-cancer therapies (e.g., chemotherapy, other targeted therapy, experimental drug, etc.) other than those administered in this study
7. Known hypersensitivity to vemurafenib or another BRAF inhibitor. In addition, for Cohort 3b only: known hypersensitivity to cetuximab
8. Prior treatment with a BRAF or MEK inhibitor (prior sorafenib is allowed)
9. Pregnant or lactating women
10. Refractory nausea and vomiting, malabsorption, external biliary shunt or significant bowel resection that would preclude adequate absorption.
11. Any of the following within the 6 months prior to first vemurafenib administration:
 - Myocardial infarction, severe/unstable angina, symptomatic congestive heart failure, cerebrovascular accident or transient ischemic attack
12. Pulmonary embolism within 30 days prior to first study medication administration
13. Hypertension not adequately controlled by current medications within 30 days prior to first study medication administration
14. History or presence of clinically significant ventricular or atrial dysrhythmias \geq Grade 2 (National Cancer Institute Common Terminology Criteria for Adverse Events, Version 4.0 [NCI CTCAE, v4.0])
15. Corrected QT (QTc) interval \geq 450 msec at baseline or history of congenital long QT syndrome or uncorrectable electrolyte abnormalities
16. Uncontrolled medical illness (such as infection requiring treatment with intravenous [IV] antibiotics)
17. Other severe, acute or chronic medical or psychiatric condition or laboratory abnormality that may increase the risk associated with study participation or study medication administration or may interfere with the interpretation of study results which, in the judgment of the Investigator, would make the patient inappropriate for entry into this study
18. Unwillingness to practice effective birth control
19. Inability to comply with other requirements of the protocol

*For prostate cancer or ECD/LCH specific eligibility criteria as part of Cohort 7, see [Appendix 9](#) and [Appendix 10](#), respectively

4.4 CONCOMITANT THERAPY

At study initiation, patients should continue with their concomitant medications, as directed by their physician, with the exception of study precluded medications (see below and [Section 4.3](#) above). All concomitant medication must be fully recorded on the eCRF. Additionally, any diagnostic, therapeutic, or surgical procedure performed during the study period should be recorded including the date, indication, description of the procedure(s) and any clinical findings.

Due to the underlying illness and the frequency of co-existent medical conditions in this patient population, all concomitant medication or treatment required by the patient will be at the discretion of the treating physician. In general, concomitant medications and therapies deemed necessary for the supportive care and safety of the patient are allowed, provided their use is documented in the patient records and on the eCRF.

For Cohort 3b only, prior to the first infusion of cetuximab, patients must receive premedication with an antihistamine and a corticosteroid. This premedication is recommended prior to all subsequent infusions. See cetuximab SPC for further details (79).

See [Appendix 9](#) for more details for prostate cancer patients.

4.4.1 Excluded Therapy and Potential Interactions with Concomitant Drugs

4.4.1.1 Excluded therapy

The following medications and treatments are not allowed while the patient is on the study:

- other anti-cancer therapies (except cetuximab for patients in Cohort 3b)
- concomitant alternative therapies and herbal preparations
- radiotherapy for the treatment of disease during the study; the exception will be limited field radiotherapy for palliative bone pain due to pre-existing bone metastasis if not considered a target lesion for RECIST assessments

However, medications primarily metabolized by CYP450 1A2, 3A4 and 2C9 enzymes, as well as those that strongly inhibit or induce the CYP 3A4 enzyme, should be used with caution when co-administered with vemurafenib.

[Appendix 2](#) includes a non-exhaustive list of typical examples of CYP1A2 and CYP3A4 substrates and CYP3A4 inducers and inhibitors.

4.4.1.2 Potential interactions with concomitant drugs

Overall, < 10% of vemurafenib was observed to be metabolized in melanoma patients in an ADME (absorption, distribution, metabolism, and excretion) study (NP25158). Preclinical studies suggest that CYP3A4 metabolism and subsequent glucuronidation are responsible for the metabolism of vemurafenib that is observed to occur in patients.

Further details on potential vemurafenib drug-drug interactions mediated via cytochrome P450 enzymes are presented below. Also presented is a brief section on potential interactions between vemurafenib and drugs that may cause QTc interval prolongation and cardiac arrhythmia.

4.4.1.2.1 CYP3A4 substrates

In the CYP450 probe study NP22676, vemurafenib induced CYP3A4 activity in melanoma patients by approximately 2-fold, as evidenced by a parent-to-metabolite AUC ratio of 2.2 for midazolam in the presence vs. the absence of vemurafenib. This interaction was statistically significantly outside the customary no-effect boundary (0.8–1.25). Thus, medications predominantly metabolized via CYP3A4 may have decreased exposure when administered concomitantly with vemurafenib.

The clinical significance of this observation depends on the therapeutic index of the specific CYP3A4 substrate administered concomitantly with vemurafenib. If CYP3A4 substrates must be co-administered with vemurafenib, the Investigator should monitor the signs of reduced benefit of CYP3A4 drugs due to potential decrease in their plasma concentration. Doses of the concomitant CYP3A4 drug, but not the dose of vemurafenib, may be adjusted as necessary to alleviate the impact of drug interaction.

[Appendix 2](#) includes a non-exhaustive list of CYP3A4 substrates.

4.4.1.2.2 CYP1A2 substrates

In the CYP450 probe study NP22676, vemurafenib inhibited CYP1A2 in metastatic melanoma patients by approximately 3-fold, as evidenced by a parent-to-metabolite AUC ratio of 0.32 for xanthine in the presence vs. the absence of vemurafenib. This interaction was statistically significantly outside the customary no-effect boundary (0.8–1.25). Similarly, other PK assessments have demonstrated drug-drug interactions between vemurafenib and caffeine that are consistent with CYP1A2 inhibition. **Thus, medications predominantly metabolized via CYP1A2 may have increased exposure when administered concomitantly with vemurafenib.**

The clinical significance of these observations depends on the therapeutic index of the specific CYP1A2 substrate administered with vemurafenib. The Investigator should assess the safety risk associated with a potential increase in plasma concentrations of any concomitantly administered, CYP1A2 metabolized drug. If there is a concern, doses of the concomitant CYP1A2 drug, but not the dose of vemurafenib, may be adjusted as necessary to alleviate the impact of drug interaction.

[Appendix 2](#) includes a non-exhaustive list of CYP1A2 substrates.

